4.5.10 Optional Samples for Research Biosample Repository

4.5.10.1 Overview of the Research Biosample Repository

The RBR is a centrally administered group of facilities used for the long-term storage of human biological specimens, including body fluids, solid tissues, and derivatives thereof (e.g., DNA, RNA, proteins, peptides). The collection, storage, and analysis of RBR *samples* will facilitate the rational design of new pharmaceutical agents and the development of diagnostic tests, which may allow for individualized drug therapy for patients in the future.

In this study, for those patients who have previously consented to the RBR in the parent studies BN29552 and BN29553 and consent to RBR in Study BN40031, all specimens for the RBR will come from retaining the residual sample remaining after the protocol-specified analysis has been performed on protocol-specified mandatory samples. These residual samples will be retained from patients who give specific consent to participate in this optional research.

RBR *samples* will be used to achieve the following objectives:

- To study the association of biomarkers with efficacy, adverse events, or disease progression
- To increase knowledge and understanding of disease biology
- To study drug response, including drug effects and the processes of drug absorption and disposition
- To develop biomarker or diagnostic assays and establish the performance characteristics of these assays

4.5.10.2 Approval by the Institutional Review Board or Ethics Committee

Collection and submission of biological samples to the RBR is contingent upon the review and approval of the exploratory research and the RBR portion of the Informed Consent Form by each site's IRB/EC and, if applicable, an appropriate regulatory body. If a site has not been granted approval for RBR sampling, this section of the protocol (Section 4.5.10) will not be applicable at that site.

4.5.10.3 Sample Collection

In the OLE study, two types of residual sample will be retained by the RBR for identification of dynamic (non-inherited) biomarkers: CSF and plasma.

- Plasma and CSF samples may be used for exploratory biomarker assays, including but not limited to determination of markers of amyloid deposition and/or clearance, markers of oxidative stress, neurodegeneration, inflammation, or other processes implicated in the pathogenesis of AD. These samples will be used to further the Sponsor's understanding of AD and the response to treatment and may also be used to support the development of biomarker and diagnostic assays.

RBR *samples* will be destroyed no later than 15 years after the date of final closure of the associated clinical database. The RBR storage period will be in accordance with the IRB/EC-approved Informed Consent Form and applicable laws (e.g., health authority requirements).

For all samples, dates of consent should be recorded on the associated RBR page of the eCRF. For sampling procedures, storage conditions, and shipment instructions, see the laboratory manual.

4.5.10.4 Confidentiality

RBR samples and associated data will be labeled with a unique patient identification number.

Patient medical information associated with *RBR samples* is confidential and may be disclosed to third parties only as permitted by the Informed Consent Form (or separate authorization for use and disclosure of personal health information) signed by the patient *or legally authorized representative*, unless permitted or required by law.

Given the complexity and exploratory nature of the analyses, data derived from *RBR samples* will generally not be provided to study investigators or patients unless required by law. The aggregate results of any conducted research will be available in accordance with the effective Sponsor policy on study data publication.

Data generated from *RBR samples* must be available for inspection upon request by representatives of national and local health authorities, and Sponsor monitors, representatives, and collaborators, as appropriate.

Any inventions and resulting patents, improvements, and/or know-how originating from the use of the *RBR* data will become and remain the exclusive and unburdened property of the Sponsor, except where agreed otherwise.

4.5.10.5 Consent to Participate in the Research Biosample Repository

The Informed Consent Form will contain a separate section that addresses participation in the *RBR*. The investigator or authorized designee will explain to each patient the objectives, methods, and potential hazards of participation in the *RBR*. Patients will be told that they are free to refuse to participate and may withdraw their specimens at any time and for any reason during the storage period. A separate *consent* will be required to document a patient's agreement to provide optional *RBR samples*. Patients who decline to participate will not provide a separate signature.

The investigator should document whether or not the patient has given consent to participate and (if applicable) the date(s) of consent, by completing the *RBR* Research Sample Informed Consent eCRF. *In participants who lack the capacity to consent, the patient's legally authorized representative may provide consent, per local requirements.*

In the event of an *RBR* participant's death or loss of competence, the participant's *samples* and data will continue to be used as part of the *RBR* research.

4.5.10.6 Withdrawal from the Research Biosample Repository

Patients who give consent to provide *RBR samples* have the right to withdraw their *consent* at any time for any reason. However, if *RBR samples* have been tested prior to withdrawal of consent, results from those tests will remain as part of the overall research data. If a patient wishes to withdraw consent to the testing of his or her *RBR samples* during the study, the investigator must inform the Medical Monitor in writing of the

patient's wishes through use of the appropriate RBR Subject Withdrawal Form and must enter the date of withdrawal on the RBR Research Sample Withdrawal of Informed Consent eCRF. *If a patient wishes to withdraw consent to the testing of his or her RBR samples after closure of the site, the investigator must inform the Sponsor by emailing the study number and patient number to the following email address:*

[contact]

A patient's withdrawal from this study does not, by itself, constitute withdrawal of consent for testing of RBR samples. Likewise, a patient's withdrawal of consent for testing of RBR samples does not constitute withdrawal from this study.

4.5.10.7 Monitoring and Oversight

RBR specimens will be tracked in a manner consistent with Good Clinical Practice by a quality-controlled, auditable, and appropriately validated laboratory information management system to ensure compliance with data confidentiality as well as adherence to authorized use of specimens as specified in this protocol and in the Informed Consent Form. Sponsor monitors and auditors will have direct access to appropriate parts of records relating to patient participation in the RBR for the purposes of verifying the data provided to the Sponsor. The site will permit monitoring, audits, IRB/EC review, and health authority inspections by providing direct access to source data and documents related to the RBR samples.

4.5.11 Timing of Visits and Study Assessments

Written informed consent for participation in the OLE study must be obtained before performing any OLE study-specific tests or evaluations *by the patient or legally authorized representative, per local requirements*. Informed Consent Forms for enrolled patients and for patients who are not subsequently enrolled will be maintained at the study site.

After giving written informed consent, patients who are willing to participate in the study will undergo assessments as per the schedule of activities (see [Appendix 1](#)).

Following *completion of the parent studies BN29552 or BN29553 Week 105 assessments and review of the Week 105 MRI results and OLE screening coagulation blood test results*, the patient's eligibility for OLE can be assessed.

If needed (e.g., for completion of Week 105 visit assessments and/or the OLE study screening coagulation blood test), an unscheduled visit can be done *after consent and before Week 1, Visit 1 of the OLE study*.

If assessed as eligible, patients may receive the first crenezumab infusion on or up to 8 weeks after the parent study Week 105 visit. Visit 1 of the OLE safety assessments

must be done on the day of infusion as indicated on the schedule of activities (see [Appendix 1](#)).

4.5.11.1 Study Assessments

The recommended order of assessments and rating scales is as follows:

- Clinical assessments (e.g., QoL-AD, ZCI-AD, MMSE, ADAS-Cog-13, ADCS-ADL, CDR), including all those that require caregiver input, should be completed before any invasive safety assessments.
- Vital signs; ECGs; and blood draws for clinical laboratory assessments, pharmacokinetics, ADA and urine samples are recommended to be collected following scale assessments and must be collected before study drug administration.

The recommended order of clinical assessments/rating scales during treatment and at the early termination visit is described in [Table 2](#).

Table 2 Order of Clinical Assessment and Rating Scale Collection

Patient	Caregiver
1. ADAS-Cog13	1. CDR (caregiver input)
2. CDR (patient interview)	2. ADCS-ADL
3. MMSE	3. FAQ
4. FCSRT ^a	4. EQ-5D-5L
5. QoL-AD	5. ZCI-AD
6. C-SSRS	6. QoL-AD
	7. NPI-Q

ADAS-Cog-13 = Alzheimer's Disease Activity Scale-Cognition 13; ADCS-ADL = Alzheimer's Disease Cooperative Study-Activities of Daily Living; CDR = Clinical Dementia Rating; C-SSRS = Columbia-Suicide Severity Rating Scale; EQ-5D-5L = EuroQoL 5-Dimension, 5-Level questionnaire; FAQ = Functional Activities Questionnaire; FCSRT = Free and Cued Serial Recall Task; MMSE = Mini Mental State Examination; NPI-Q = Neuropsychiatric Inventory-Questionnaire; QoL-AD = Quality of Life-Alzheimer's Disease; ZCI-AD = Zarit Caregiver Interview for Alzheimer's Disease.

^a If appropriate per schedule of activities.

If assessments are split over 2 days, all safety assessments must be done on same day as the infusion.

4.6 TREATMENT, PATIENT, STUDY, AND SITE DISCONTINUATION

4.6.1 Study Treatment Discontinuation

Patients must permanently discontinue study treatment if they experience any of the following:

- Pregnancy

- Evidence of more than 15 *ARIA-H* (microbleeds and/or areas of leptomeningeal hemosiderosis) including any present at baseline, as assessed by central review of MRI
- Diagnosed with three recurrent, symptomatic *ARIA-E* events or exacerbations of previous events

The primary reason for study treatment discontinuation should be documented on the appropriate eCRF. Patients who discontinue study treatment prematurely will not be replaced.

All patients who discontinue from the study treatment early will be asked to return at 4 and 16 weeks from the time of the last dose of study treatment for safety assessments. Patients that discontinue before Week 105 will also be asked to return for their next scheduled annual assessment (Week 53 or Week 105). If the next annual follow-up visit (Week 53 or *Week* 105) is expected within 3 months of the 4-week safety visit, the annual and 4-week safety visits can be combined.

4.6.2 Patient Discontinuation

Patients have the right to voluntarily withdraw from the study at any time for any reason. In addition, the investigator has the right to withdraw a patient from the study at any time. Reasons for withdrawal from the study may include, but are not limited to, the following:

- Patient withdrawal of consent at any time
- Any medical condition that the investigator or Sponsor determines may jeopardize the patient's safety if he or she continues in the study
- Investigator or Sponsor determines it is in the best interest of the patient

Patients should be informed of circumstances under which their participation may be terminated by the investigator without the patient's consent. Any administrative or other reasons for withdrawal must be explained to the patient.

Every effort should be made to obtain information on patients who withdraw from the study. The primary reason for withdrawal from the study should be documented on the appropriate eCRF. However, patients will not be followed for any reason after consent has been withdrawn. Patients who withdraw from the study will not be replaced.

4.6.3 Study Discontinuation

The Sponsor has the right to terminate this study at any time. Reasons for terminating the study may include, but are not limited to, the following:

- The incidence or severity of adverse events in this or other studies indicates a potential health hazard to patients.
- Patient enrollment is unsatisfactory.
- Futility analyses from this or other studies with crenezumab suggest that treatment with crenezumab is likely not effective.

- Sponsor determines it is in the best interest of the patients.

The Sponsor will notify the investigator if the study is placed on hold or if the Sponsor decides to discontinue the study or development program.

4.6.4 Site Discontinuation

The Sponsor has the right to close a site at any time. Reasons for closing a site may include, but are not limited to, the following:

- Excessively slow recruitment
- Poor protocol adherence
- Inaccurate or incomplete data recording
- Non-compliance with the International Council for Harmonisation (ICH) guideline for Good Clinical Practice
- No study activity (i.e., all patients have completed the study and all obligations have been fulfilled)

5. ASSESSMENT OF SAFETY

5.1 SAFETY PLAN

Crenezumab is not approved, and clinical development is ongoing. The safety plan for patients in this study is based on clinical experience with crenezumab in completed and ongoing studies. The anticipated important safety risks for crenezumab are outlined below. Refer to the Crenezumab Investigator's Brochure for a complete summary of safety information.

Several measures will be taken to ensure the safety of patients participating in this study. Eligibility criteria have been designed to exclude patients at higher risk for toxicities. Patients will undergo safety monitoring during the study, including assessment of the nature, frequency, and severity of adverse events. In addition, guidelines for managing adverse events, including criteria for dosage modification and treatment interruption or discontinuation, are provided below.

Investigators will assess the occurrence of adverse events and serious adverse events at all patient evaluation timepoints during the study. All adverse events and serious adverse events, whether volunteered by the patient, discovered by study personnel during questioning, or detected through physical examination, laboratory test, or other means, will be recorded in the patient's medical record and on the appropriate adverse event eCRF. Each recorded adverse event or serious adverse event will include a description of its duration (i.e., start and end dates), severity, seriousness according to regulatory criteria, if applicable, and suspected relationship to the investigational product, as well as any actions taken. Patients will be carefully followed for adverse events during the study, including a safety follow-up period of 16 weeks after the last dose of study drug.

An iDMC will review unblinded safety and efficacy data at regular intervals (see Section 3.2.1 and the iDMC Charter for further details).

5.1.1 **ARIA-E and ARIA-H**

The occurrence of imaging abnormalities believed to represent ARIA-E has been reported in association with the investigational use of compounds that are intended to treat AD through the reduction of A β in the brain. These imaging abnormalities have, in the majority of instances, been asymptomatic, and their presence has been detected by brain MRI (Salloway et al. 2009; Sperling et al. 2011). These MRI signal hyperintensities seen in the parenchyma and leptomeninges are named ARIA-E to cover the MRI alterations seen in the fluid-attenuated inversion recovery sequence thought to represent edema in the gray and white matter and effusion or extravasated fluid in the sulcal space (Sperling et al. 2011). Symptoms, when present in association with such imaging abnormalities, have been reported to include headache, worsening cognitive function, alteration of consciousness, seizures, unsteadiness, and vomiting.

Cerebral mHs in AD have a point prevalence of 23% (Vernooij et al. 2008). One longitudinal study found that in patients with AD the incidence of ≥ 1 mH after a mean follow-up of 2 years was 12% (Goos et al. 2010). Recently, the occurrence of mH has also been identified as an adverse event in anti-amyloid vaccination trials, and together with superficial siderosis, these events have been termed ARIA-H deposition (Sperling et al. 2011).

Limited data on ARIA-H deposition occurrence are available, but a retrospective analysis in patients with AD who were treated with anti-A β antibodies with full effector function reported that 24 of 207 patients (11.6%) developed ARIA-H deposition (Sperling et al. 2012). Acute occurrence of cerebral mH is not always considered clinically significant (Greenberg et al. 2009). Study patients who received bapineuzamab and developed ARIA-H deposition without ARIA-E were clinically asymptomatic (Sperling et al. 2012). However, the clinical significance of cerebral mH is not yet fully understood.

Recent population-based studies have shown that cerebral mHs are common in community-dwelling elderly people, with high prevalence ranging from 10%–25% (Greenberg et al. 2009). Among those patients, approximately 70%–80% had 1 or 2 cerebral mHs (Cordonnier and van der Flier 2011) and high numbers of cerebral mHs have been associated with future risk of ischemic and hemorrhagic strokes (Greenberg et al. 2009). In a longitudinal study in patients visiting a memory clinic, the incidence of new cerebral mHs (range, 1–19 per patient) within 2 years of that visit was approximately 12%, and the incidence was not related to diagnosis (type of dementia or disease severity) or APOE4 status (Goos et al. 2010). Taken together, accumulating evidence suggests that cerebral mHs are common in cross-sectional observational studies of healthy elderly subjects, and the increase in prevalence over time may be part of the natural history of aging, which indicates a

specific underlying vascular pathologic state, in particular hypertensive vasculopathy or cerebral amyloid angiopathy.

When anti-A β antibodies bind to amyloid deposited around blood vessels, an Fc γ R-mediated immune response may be elicited. This compromises vascular integrity and results in ARIA-E or ARIA-H deposition. The hypothesis that Fc γ R-mediated immune response may contribute to the occurrence of ARIA-E and/or ARIA-H deposition is supported by results from clinical studies that have shown that patients with AD who were treated with anti-A β antibodies with full effector function developed ARIA-E (symptomatic and asymptomatic) that were dependent on the dose level and related to APOE4 status.

Crenezumab, a human IgG4, has reduced Fc γ R binding compared with IgG1/IgG2 and, thus, has reduced effector function that theoretically might lower the risk of ARIA-E. This has been supported by emergent safety data observed in both clinical and nonclinical studies. In the completed Phase I and II studies, only a single case of ARIA-E has been observed as of 27 May 2016 (a case of asymptomatic sulcal effusion observed in the intravenous cohort of Study ABE4869g in a patient treated with crenezumab). This same patient had recurrences of ARIA-E effusion during the corresponding OLE study.

Since development of asymptomatic cerebral mHs may occur within the natural history of AD at a rate of approximately 10% per year, the appearance of new cerebral mHs should not automatically disqualify a patient from further treatment. However, as the occurrence of new cerebral mHs may also result from amyloid clearance associated with amyloid-lowering therapy and high numbers of new cerebral mHs might impose a risk for future ischemic and hemorrhagic strokes, study drug must be discontinued in specific circumstances (see Section 5.1.2 for details of withdrawal rules).

In this Phase III OLE study, a safety monitoring plan has been designed to monitor the potential risk of ARIA-E and ARIA-H deposition. This plan consists of the following key elements:

- Exclusion criteria:
 - Evidence of > 10 ARIA-H (microbleeds and/or areas of leptomeningeal hemosiderosis) as assessed by central review of T2* gradient-recalled echo MRI (see Magnetic Resonance Imaging Charter for further details)
- Prior to all MRI evaluations, the patient or caregiver will be contacted to determine if the patient has any CNS-related symptoms. If present, a symptom-led assessment will be performed at the visit.
- Brain MRI (including fluid-attenuated inversion recovery sequence and T2*-weighted gradient-recalled echo sequences) will be performed *at Weeks 13, 25, 53, 105, and yearly thereafter* to detect ARIA-E and ARIA-H deposition.

- All MRI scans will be read in a timely fashion and will evaluate ARIA-E and ARIA-H deposition as well as other abnormalities. Assessments will be made by independent blinded radiologists at a central contract imaging vendor.
- Patients who exhibit new ARIA-E (but do not qualify for treatment discontinuation as defined below) will be rescanned within approximately 4 weeks after the last MRI scan to evaluate the evolution of the findings.

ARIA-E or ARIA-H deposition findings that lead to dose modification or treatment discontinuation and study drug discontinuation rules in specific cases are detailed in Section [5.1.2](#).

5.1.2 ARIA-Related Dose Adjustments

The following dose adjustments and discontinuation rules for MRI-related findings will apply.

5.1.2.1 ARIA-E

Asymptomatic ARIA-E with Barkhof Grand Total Score < 4 (Barkhof et al. 2013):

- Continue study drug at the same dose (i.e., 60 mg/kg crenezumab)
- Repeat magnetic resonance imaging 4 weeks later
 - If ARIA-E is stable or decreased, continue study drug and monthly MRI monitoring until event resolves. Once ARIA-E completely resolves, conduct MRI monitoring as per Section [4.5.9](#).
 - If ARIA-E increases (Barkhof Grand Total Score ≥ 4) or symptoms develop, refer to the rule below.

Symptomatic ARIA-E (any size) or ARIA-E with Barkhof Grand Total Score ≥ 4 :

- Temporarily interrupt study drug and implement monthly MRI monitoring
- Once symptoms and ARIA-E resolve, reintroduce study drug at the same dose (i.e., 60 mg/kg crenezumab) and perform an MRI after 4 weeks of dosing. If no new ARIA-E is detected, MRI monitoring as per Section [4.5.9](#).

Any new onset of ARIA-E: Treat the same as the first event on the basis of symptoms and Barkhof Grand Total Score. However, **in the case where a patient is diagnosed with three recurrent, symptomatic ARIA-E events or exacerbations of previous events, permanently discontinue the study drug**. Implement monthly MRI monitoring until resolution of both symptoms and ARIA-E. As per the protocol, maintain the patient in the study until study end and perform assessments as per the schedule of activities.

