4.3.2.1 Crenezumab

Crenezumab will be administered via IV infusion to all patients at a dose of 60 mg/kg Q4W until the end of the study (see Section 3.3).

All IV infusions of crenezumab will be administered by appropriately trained staff in the clinic or other agreed environment (e.g., the patient's home if that option becomes available at a later time). The first four infusions of study drug must be administered at the clinic for all patients as a minimum.

The IV drug will be prepared and infused from the IV bag by infusion pump. The bag size, drug preparation, and infusion rates are all described in the pharmacy manual. All patients will be monitored for a minimum of 1 hour after dosing, and vital signs will be measured immediately following completion of the infusion and ≥ 60 minutes after the end of the infusion as described in the pharmacy manual.

For the IV dose calculation, the patient's weight at Week 105 of Study BN29552 or BN29553 (reference weight) should be used. If the current weight changes by $\geq 10\%$, the current weight should become the new reference weight for subsequent dosing. If the patient's weight changes again by $\geq 10\%$ from the reference weight, the IV dose should again be recalculated. See the pharmacy manual for further information.

Crenezumab will be administered to patients under close medical supervision in a setting with access to appropriate emergency equipment and staff who are trained to monitor and respond to medical emergencies. In the event that a patient experiences a mild infusion-related reaction, the infusion will be halted. Once the reaction has resolved, the infusion rate will be resumed at half of the most recently used rate

Patients who experience a moderate infusion-related

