5.1.2.2 ARIA-H

Dose reduction: Patients who develop >10 ARIA-H cumulatively will receive a lower dose of the study drug. Of note, patients who received a reduced dose of blinded study drug can start the OLE phase with the full dose of 60 mg/kg crenezumab.

Study drug discontinuation: Patients who develop > 15 ARIA-H cumulatively will be permanently discontinued from the study drug.

Cumulative ARIA-H is the sum of ARIA-H at baseline (of Study BN29552 or BN29553) and newly detected ARIA-H during the studies.

The rules in Sections 4.1.2 and 5.1, coupled with frequent MRI monitoring and collection of CNS symptoms, are put in place by the Sponsor to ensure safety while maximizing benefit for patients.

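### The ARIA-E rules fix the dose at 60 mg/kg while the ARIA-H rule requires a lower one, so a patient with ARIA-E and 11 to 15 cumulative ARIA-H has two instructions that cannot both be followed

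*Combined protocol and SAP*

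**What the plan says.** Section 5.1.2 introduces the ARIA-E and ARIA-H rules together and says that they apply.

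Section 5.1.2.1 (ARIA-E) has two dosing branches:

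- Asymptomatic, Barkhof Grand Total Score below 4: "Continue study drug at the same dose (i.e., 60 mg/kg crenezumab", with a repeat MRI.
- Symptomatic, or score of 4 or more: interrupt drug and then, once symptoms and imaging findings have resolved, "reintroduce study drug at the same dose (i.e., 60 mg/kg crenezumab".

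For later events the instruction is "Treat the same as the first event on the basis of symptoms and Barkhof Grand Total Score". The one exception is permanent discontinuation after three recurrent symptomatic events or exacerbations.

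Section 5.1.2.2 (ARIA-H) has two thresholds. The first is "Patients who develop >10 ARIA-H cumulatively will receive a lower dose of the study drug". The second is "Patients who develop > 15 ARIA-H cumulatively will be permanently discontinued from the study drug". The count is defined as follows: "Cumulative ARIA-H is the sum of ARIA-H at baseline (of Study BN29552 or BN29553) and newly detected ARIA-H during the studies". The subsection does not give the amount of the lower dose. It adds that "patients who received a reduced dose of blinded study drug can start the OLE phase with the full dose of 60 mg/kg crenezumab".

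Section 4.3.2.1 gives the general regimen for all patients, "at a dose of 60 mg/kg Q4W until the end of the study".

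**The concern.** Neither ARIA subsection mentions the other. A patient can meet both rules in two ways: by being reduced for ARIA-H and developing ARIA-E later, or by having both findings on one scan. The second route is realistic, because Section 5.1.1 uses the same scheduled MRIs (Weeks 13, 25, 53, 105 and yearly) to look for both.

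In the first case, the words for an unchanged dose and the figure of 60 mg/kg disagree with each other. In the second, one subsection lowers the dose and the other holds it at 60 mg/kg.

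What is at stake is a dosing decision in a patient with two imaging safety findings. Whichever instruction the site follows departs from the other, and Section 9.2 does not allow prospective requests to deviate from the protocol. Section 3.1 expects about 350 centers in about 40 countries, so the text needs to settle the matter by itself.

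**Working it through.** There is no planned figure to reproduce. Section 6.1 states that the sample size has no formal calculation, and this point does not depend on one. The check is a comparison of the rules, followed by a look at what the documents say about frequency.

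**Step 1: where the rules overlap.** The reduction rule starts above 10 and the discontinuation rule above 15, so the reduced-dose range is 11 to 15 cumulative ARIA-H. Section 4.1.2 excludes patients with more than 10 at the parent-study Week 105 MRI, so the relevant counts are those reached during the extension.

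| Cumulative ARIA-H | ARIA-E | Section 5.1.2.1 | Section 5.1.2.2 | Can both be followed? |
|---|---|---|---|---|
| 10 or fewer | Any | 60 mg/kg, at once or after resolution | No change | Yes |
| 11 to 15 | Asymptomatic, score below 4 | Continue at 60 mg/kg | Lower dose | No, from the first decision |
| 11 to 15 | Symptomatic, or score 4 or more | Interrupt, then 60 mg/kg after resolution | Lower dose | Yes during interruption; no at reintroduction |
| More than 15 | Any | As above | Permanent discontinuation | Section 4.6.1 separately requires discontinuation, so no dose has to be chosen |

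Three recurrent symptomatic ARIA-E events or exacerbations also lead to permanent discontinuation at any ARIA-H count, which removes those patients from the conflict.

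**Step 2: is there an exception elsewhere?** Sections 4.3.2.1, 4.6.1, 5.1, 5.1.1, 5.1.2 and 5.1.3.2 give neither an exception nor an order of precedence. The one sentence that relates a reduced dose to 60 mg/kg concerns starting the extension after a reduced blinded dose. It does not cover ARIA-E in a patient reduced during the extension.

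**Step 3: how often?** The documents give the two findings separately, never jointly.

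- ARIA-E in Phase II (Section 1.2.3): 1/349 = 0.29% of crenezumab patients.
- Any incident microhemorrhage in Phase II: 40/349 = 11.5%. This is any new finding, not more than 10 cumulative. Section 5.1.1 says that about 70% to 80% of community-dwelling elderly people with microhemorrhages had only 1 or 2.
- ARIA-E across the whole program: 4 patients, with about 1051 people exposed to crenezumab (Section 1.2.2). Carried over crudely to the expected 925 extension patients, 4 × 925/1051 = 3.5 patients with any ARIA-E. Only those who also have 11 to 15 ARIA-H would meet the conflict.

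Multiplying the Phase II rates gives 0.0029 × 0.115 × 925 = 0.3 patients, but this is not a usable estimate. It assumes that the findings are independent, uses the wrong ARIA-H threshold, and comes from doses whose exposure was, at the higher of the two, about a quarter of that at 60 mg/kg (Section 1.3.4). The first and third could make it too low, and the second makes it too high.

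**The case against.** The best case for the text as it stands is that the two subsections can be read together. On that reading, ARIA-E alone does not change the dose, the parenthesis merely names the study's standard dose, and Section 5.1.2.2 is the only place where a dose is reduced. A patient already reduced for ARIA-H would then simply stay on the current dose.

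This may be what was intended, but it is not what is written. The parenthesis defines the dose as 60 mg/kg, and Section 5.1.2.2 uses that figure for the full dose as opposed to a reduced one: "patients who received a reduced dose of blinded study drug can start the OLE phase with the full dose of 60 mg/kg crenezumab". The figure is therefore not shorthand for whatever the patient is receiving.

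Other parts of the case against do stand, and they limit the point:

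- A reader might infer that Section 4.3.2.1 is a third contradictory instruction. It is a general regimen. Section 5.1 says that dose-modification criteria follow, and Section 5.1.1 sends the reader to Section 5.1.2 for them.
- A reader might infer that these patients' ARIA events would be reported as events on 60 mg/kg whatever was given. No section says so. Section 6.4 groups patients by treatment received until the first extension visit, that is, by parent-study treatment. Section 6 refers to actual treatment received, and Section 6.5.4 allows exposure-safety analyses.
- It is not known that sites would in fact dose differently. The pharmacy manual is not available for this review, although the ARIA rules do not refer to it for this case.

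**Conclusion.** The inconsistency is real and narrow. It covers patients with 11 to 15 cumulative ARIA-H during the extension who also have ARIA-E. It takes effect at once for asymptomatic ARIA-E with a Barkhof score below 4, and only at reintroduction for the rest.

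Few patients, possibly none, are expected to meet it. A reader might be tempted to put a count on this, but the documents give no joint frequency and no rate for more than 10 ARIA-H, so no number of affected patients can be defended.

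The conclusion rests on the wording of Sections 5.1.2, 5.1.2.1 and 5.1.2.2 alone. It would change only if a document not seen here, such as the pharmacy manual, sets an order of precedence. Even then, the protocol should point to it. Nothing here shows a fault in the planned safety analysis. The point is worth acting on because it concerns dosing after two imaging safety findings and is cheap to correct. No view is taken on which dose is right.

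**What to change.** The sponsor's clinical team should reconcile Sections 5.1.2.1 and 5.1.2.2 and state which instruction governs when ARIA-E occurs in a patient who meets, or has already met, the ARIA-H reduction rule. The statement should cover both the continuation branch and the reintroduction branch. Each subsection should then refer to the other. A pointer from Section 4.3.2.1 to Section 5.1.2 would help but is optional.

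The cost is a few sentences in the next amendment, with no new data collection. No change to Section 6.4 follows from this point; tabulating adverse events by dose at onset would be a preference.
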